12.3 RADAR Score

The antibiotic use will be defined as number of days with antibiotic treatment (DOT, aggregate sum of days for which any amount of a specific antibiotic is given, eg. if 2 different antibiotics for 5 days, DOT = 10 / days in ICU.

[figure not shown]
12.4 Sample Size and Justification

DOOR-RADAR requires fewer patients than conventional non-inferiority analysis but since a major objective of this study is to enable a detailed analysis of adverse events related to antibiotic use, we have calculated a sample size that would enable separate analysis of clinical outcomes and antibiotic use (Sample size calculations detailed in Appendix I).

Testing hypothesis 1 (H1): We desire at least 80% power to test our primary hypothesis that BV-supported antibiotic treatment decision can lead to reducing antibiotic exposure using a one-sided significance of 0.05. Demonstrating H1 would require a sample size of 352 participants per group for a mean difference in antibiotic days of 1.5 (SD 8 days). Based on studies evaluating AMS interventions in the ICU, we estimate a 1.5 days difference between the 2 groups to be significant^{14,18,36}. Further, it would be equivalent to a 20% decrease in total antibiotic days, a reasonable assumption considering antibiotics are “clearly not indicated” or “only somewhat (dubious) indicated” in about 30% of cases based on prior retrospective audits of prescription quality.

Testing hypothesis 2 (H2): BV-supported antibiotic treatment algorithm does not lead to worse clinical outcomes. Studies using combined endpoints of adverse outcomes have estimated between 10-25% rates of combined adverse outcomes (death, septic shock, mechanical ventilation, renal failure)^{38,42,43}. A meta-analysis of PCT-guided antibiotic treatment in patients with infection and sepsis in ICU reported all-cause mortality rates of 23% at 30-days³⁵. Studies evaluating adverse events specifically related to antibiotic use in hospitalized patients suggest rates of 12% within 30 days. We expect a combined adverse outcome rate of 18-20% and will set a non-inferiority margin at 4%. A sample size of 529 patients per group (1060 in total) will therefore provide 80% power to demonstrate H2 (a robust safety evaluation), and yet be exceptionally well powered for efficacy (with preserved power under a wide range of assumptions).

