4.1 Number of Participants

Our target recruitment goal is 600 participants per group (1200 total participants) at participating MUHC sites.

During the pilot phase of the study, it was documented that the study population in ICU are often incapable of providing informed consent for themselves due to their health condition or due to the fact they are intubated. As of 17-Jun-2025, 40% of otherwise eligible patients could not be approached by the research team as they suddenly lost their capacity to consent for themselves. Without the possibility to approach the Legally Authorized Representative who makes health decisions on behalf of the patient, there is a significant risk the BAST-ICU trial may not meet its enrollment target therefore study objectives.

As this study represents minimal risks to participants, that medical decision-making remains in the treating team's hands, and the objectives of the study would not be met if only patients with capacity to consent are approached, the inclusion criteria are updated to include:

- Participant who have suddenly lost capacity to consent due to their health condition (intensive care) and for whom a Legally Authorized Representative can be approached and provide consent for the patient. The research team will seek the participant's consent (confirmation of consent or withdrawal) as soon as the participant regains capacity to consent.

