7. RANDOMIZATION AND BLINDING PROCEDURES

7.1 Randomization

Eligible participants will be randomized in a 1:1 ratio to either the intervention or control groups. Randomization will be stratified by study center to account for site-specific participant characteristics and physician practices. This stratification ensures that any potential confounding factors associated with the different sites are balanced across the treatment groups.

To further ensure the randomization process is robust, block randomization will be utilized within each site. The blocks will have varying sizes, determined by an internet-based randomization tool, to prevent predictability and maintain the integrity of the allocation process. The specific block sizes will remain undisclosed to the research team and participants to ensure concealment and prevent potential bias.

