12.5 Expected Study Recruitment Flow Chart

12.6 Estimations of Adverse Outcomes in ICU

- Combined severe (Grade IV) adverse events secondary to antibiotics (excluding renal): 5-10%
- Overall Acute kidney injury in ICU (all cause): 26-67%
- Drug induced liver injury: rare (16-19/100,000)
- All cause ICU Mortality: 3-28% (MUHC ICU mortality: 13%; median length of stay in (IQR): 3.2 days (1.5, 7.6))

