57. Howard-Anderson, J. *et al.* Moving Beyond Mortality: Development and Application of a Desirability of Outcome Ranking (DOOR) Endpoint for Hospital-Acquired Bacterial Pneumonia and Ventilator-Associated Bacterial Pneumonia. *Clin. Infect. Dis.* ciad576 (2023) doi:10.1093/cid/ciad576.
58. Howard-Anderson, J. *et al.* Improving Traditional Registrational Trial End Points: Development and Application of a Desirability of Outcome Ranking End Point for Complicated Urinary Tract Infection Clinical Trials. *Clin. Infect. Dis.* **76**, e1157–e1165 (2023).
59. Doernberg, S. B. *et al.* Good Studies Evaluate the Disease While Great Studies Evaluate the Patient: Development and Application of a Desirability of Outcome Ranking Endpoint for Staphylococcus aureus Bloodstream Infection. *Clin. Infect. Dis.* **68**, 1691–1698 (2019).
60. Tamma, P. D., Avdic, E., Li, D. X., Dzintars, K. & Cosgrove, S. E. Association of Adverse Events With Antibiotic Use in Hospitalized Patients. *JAMA Intern. Med.* **177**, 1308–1315 (2017).
61. DeMets, D. L. & Lan, K. K. G. L an- DE METS Alpha-Spending Function. in *Wiley Encyclopedia of Clinical Trials* (eds. D’Agostino, R. B., Sullivan, L. & Massaro, J.) 1–10 (Wiley, 2008). doi:10.1002/9780471462422.eoct394.
62. Schröder, W. *et al.* Gender differences in antibiotic prescribing in the community: a systematic review and meta-analysis. *J. Antimicrob. Chemother.* **71**, 1800–1806 (2016).
63. Smith, D. R. M., Dolk, F. C. K., Smieszek, T., Robotham, J. V. & Pouwels, K. B. Understanding the gender gap in antibiotic prescribing: a cross-sectional analysis of English primary care. *BMJ Open* **8**, e020203 (2018).

64. Young, E. H. *et al.* National Disparities in Antibiotic Prescribing by Race, Ethnicity, Age Group, and Sex in United States Ambulatory Care Visits, 2009 to 2016. *Antibiotics* **12**, 51 (2022).

18. Appendix I: Sample Size Calculations

For all calculations below – Type I error = 0.05, Power = 0.8, One-sided test

Sample size required for Hypothesis 1 that BV-supported antibiotic treatment recommendation leads to reducing antibiotic exposure.

Expected difference in mean # of days on antibiotics	Standard deviation of Days of antibiotics in ICU	Sample size required per group
1.5 days	10 days	550
1.5 days	8 days	352
1.5 days	6 days	198
1.5 days	4 days	89

Sample size required for Hypothesis 2 that BV-guided antibiotic treatment recommendation does not lead to worse clinical outcomes.

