Risk of adverse events in BV group	Risk of adverse events in control group	Non-inferiority margin	Sample size required Per group
32%	30%	4%	6612
30%	30%	4%	1624
28%	30%	4%	708
22%	20%	4%	5128
20%	20%	4%	1238
18%	20%	4%	529
17%	15%	4%	4154
15%	15%	4%	986
13%	15%	4%	414

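### The 80% power stated for the safety hypothesis H2 assumes, without saying so in Section 12.4, that the BV arm truly has 2 points fewer adverse outcomes; with equal 20% rates it is about 49% at 529 per group and 53% at 600

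*Protocol*

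**What the plan says.** Section 12.4 words H2 as follows: "BV-supported antibiotic treatment algorithm does not lead to worse clinical outcomes". It then gives one range for the event rate, together with the margin: "We expect a combined adverse outcome rate of 18-20% and will set a non-inferiority margin at 4" (per cent). From these it draws its conclusion: "A sample size of 529 patients per group (1060 in total) will therefore provide 80% power to demonstrate H2 (a robust safety evaluation".

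Section 12.4 refers to Appendix I for the details. The appendix sets the error rates for all its calculations: "Type I error = 0.05, Power = 0.8, One-sided test". Its Hypothesis 2 table has separate columns for the BV and control risks. With 20% in control and a 4% margin, it lists these sizes per group:

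| BV risk | Control risk | n per group |
|---|---|---|
| 22% | 20% | 5128 |
| 20% | 20% | 1238 |
| 18% | 20% | 529 |

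Enrolment is set above 529 per group in Section 4.1: "Our target recruitment goal is 600 participants per group (1200 total participants". Section 7.1 fixes 1:1 allocation.

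**The concern.** Read by itself, Section 12.4 presents 18-20% as one rate expected in the trial and derives 80% power from that rate and the margin. The appendix shows that the two ends of the range belong to different arms, with the lower one in the BV arm. The conclusion therefore needs a third input that Section 12.4 does not state: that BV reduces adverse outcomes by 2 percentage points. In a non-inferiority calculation this input matters a great deal, because it widens the distance between the true difference and the margin from 4 points to 6.

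The protocol gives no argument for such a benefit. H2 is worded as not worse in Section 12.4 and as no significant difference in Section 12.8. Section 1.3 anticipates less antibiotic use without loss of safety, not a gain in safety.

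H2 is the formal safety test, and under Section 12.8 the decision to continue rests on it once H1 has been rejected at the first interim analysis. The ethics board, the data safety committee and later readers are told that this test is robustly powered. If BV is exactly as safe as control, the test would miss its margin in nearly half of such trials.

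**Working it through.** **Inputs.** One-sided alpha 0.05 and power 0.80 (Appendix I); margin 0.04 (Section 12.4); arm-specific risks (Appendix I, Hypothesis 2 table); 529 per group (Section 12.4) and 600 per group (Section 4.1); 1:1 allocation (Section 7.1).

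**Formulas** (unpooled normal approximation), with pB and pC the true risks in the BV and control arms:

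- V = pB(1 − pB) + pC(1 − pC)
- distance to the margin: d = 0.04 − (pB − pC)
- n per group = (1.645 + 0.842)² × V / d²
- power = Φ(d / √(V/n) − 1.645)

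**Step 1: reproduce the plan's figure.** For BV 18% and control 20%, V = 0.1476 + 0.1600 = 0.3076 and d = 0.06. Then n = 6.183 × 0.3076 / 0.0036 = 528.3, rounded up to 529. Power at 529 is 80.05%. The sum behind 529 is right, and all nine rows of the Hypothesis 2 table reproduce to within 2 patients.

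**Step 2: remove the assumed benefit.** For 20% in both arms, V = 0.32 and d = 0.04. Then n = 6.183 × 0.32 / 0.0016 = 1236.5, rounded up to 1237, against 1238 in the protocol's table. That is about twice the planned 600.

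**Step 3: power at the sizes the protocol gives.**

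- 529 per group, 20% in both arms: √(0.32/529) = 0.02459; 0.04/0.02459 − 1.645 = −0.018; power 49%.
- 600 per group, 20% in both arms: √(0.32/600) = 0.02309; 0.04/0.02309 − 1.645 = 0.087; power 53%.

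The same formula at 600 per group gives:

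| BV risk | Control risk | d | Power, n = 600 |
|---|---|---|---|
| 18% | 20% | 0.06 | 84% |
| 19% | 20% | 0.05 | 71% |
| 18% | 18% | 0.04 | 56% |
| 19% | 19% | 0.04 | 55% |
| 20% | 20% | 0.04 | 53% |
| 22% | 20% | 0.02 | 21% |

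Simulation with 400,000 replicates per scenario agrees: 80.1% (529, 18% v 20%), 49.3% (529, 20% v 20%), 84.3% (600, 18% v 20%), 53.6% (600, 20% v 20%) and 56.5% (600, 18% v 18%).

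**Step 4: is the result sensitive to where in 18-20% the common rate lies?** No. With equal rates anywhere in that range, 600 per group gives 53-56%, and 80% power needs 1141 to 1237 per group.

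**The case against.** **The appendix discloses the assumption.** Section 12.4 points to Appendix I, where the two risks are labelled by arm and the equal-rate and BV-worse rows are printed. The range may just be a poor rendering of 18% against 20%. This is fair as far as it goes: the inputs can be found. But neither place says that the row with a BV benefit was chosen, or why, and Section 12.4 states its conclusion as following from the rate and the margin alone.

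**A small benefit is a legitimate planning assumption.** A reader might infer that H2 asserts equal rates, so that any assumed benefit is an error. The documents do not support that: not worse covers equal or better. A benefit is also conceivable on the protocol's own figures. Section 12.4 equates the target difference with a 20% fall in antibiotic days. If antibiotic-related events fell in proportion (an assumption made here, not in the protocol), 20% of the 5-10% Grade IV rate in Section 12.6 is 1 to 2 points, and 20% of the 12% rate in Section 12.4 is 2.4 points. This stands in part. However, the protocol does not make the argument, it requires that stopping antibiotics causes no offsetting harm, and 2 points lies towards the upper end of that range. At 1 point, power at 600 per group is 71%.

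**The event rate.** A reader might add the mortality and Grade IV figures and infer that 18-20% is itself too low. That does not hold up. Combining the 13% local ICU mortality with 5-10% Grade IV events among survivors gives 0.13 + 0.87 × (0.05 to 0.10) = 17% to 22%, a range that contains 18-20%. The 23% mortality in Section 12.4 comes from patients with infection and sepsis in procalcitonin trials, a different population from the one enrolled here. The point made here does not depend on the event rate being wrong.

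**H2 is not the whole primary outcome.** The synopsis names DOOR and RADAR as primary, and H2 is a separate analysis. That is so, but Section 12.4 bases the sample size on separate tests of H1 and H2, and Section 12.8 gives H2 a role in the decision to continue.

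**Conclusion.** The concern holds as a fault in how the power is stated. The 80% at 529 per group is conditional on a true 2-point benefit that Section 12.4 does not state and the protocol does not justify. Without that benefit, at 20% in both arms, power is about 49% at 529 and about 53% at 600; over the protocol's own 18-20% range it is 53-56% at 600.

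These figures rest on one-sided 0.05, the 4-point margin, the normal approximation, and all patients being evaluable. They make no allowance for the two interim analyses. Under O'Brien-Fleming-type spending at one third and two thirds of enrolment (an assumption, since the protocol does not give the spending function), they stay at about 84% and 53%. Missing outcomes would lower them.

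Two stronger readings should be resisted. This is not an arithmetic error, because 529 is correct for its inputs. Nor do the documents show that a missed margin would be taken as harm: Section 1.3 ties its negative recommendation to evidence of harm, and how to report an inconclusive H2 may be left to the statistical analysis plan.

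**What to change.** Replace the power sentence for H2 in Section 12.4 with wording such as:

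> *With 600 participants per group, a 4-point margin and a one-sided 0.05 level, power for H2 is 84% if the true adverse outcome rate is 18% in the BV arm and 20% in control, and about 53% if it is 20% in both arms.*

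In the same place, replace the 18-20% range with the rate assumed for each arm. Either delete the description of H2 as a robust safety evaluation or make it explicitly conditional on the 2-point benefit. If the sponsor wishes to keep that benefit as the planning assumption, a sentence giving the reason for it belongs there too.

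The cost is protocol wording and a less favourable stated power. The sample size, margin and enrolment target can stay as they are, and no extra patients are needed.

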12.5 Expected Study Recruitment Flow Chart

12.6 Estimations of Adverse Outcomes in ICU

- Combined severe (Grade IV) adverse events secondary to antibiotics (excluding renal): 5-10%
- Overall Acute kidney injury in ICU (all cause): 26-67%
- Drug induced liver injury: rare (16-19/100,000)
- All cause ICU Mortality: 3-28% (MUHC ICU mortality: 13%; median length of stay in (IQR): 3.2 days (1.5, 7.6))

12.7 Primary Analysis

The primary analysis will be an intent-to-treat (ITT) and will include 2 interim analyses at 1/3 and 2/3 enrolment. The final analysis will use Lan-DeMets stopping rules⁶². We will also perform per-protocol analyses where the treatment recommendations were followed.

12.8 Frequency of Analyses

Our approach for interim monitoring is to test H1 first (null H1: no difference between intervention and control in terms of antibiotic exposure). Should the null H1 be rejected at the first interim, then the second hypothesis (H2: no significant difference in combined endpoint of adverse events between the 2 groups) will be assessed and decision to continue will be based on H2. If H1 is not rejected at the interim, then H2 will not be assessed until the final analysis. We estimate that H1 testing may cross the pre-specified boundary at one of the interim analyses, but H2 testing may only meet non-inferiority once full sample size is enrolled.

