1.3 Potential impact

We anticipate this study will demonstrate that an evidence-based implementation strategy of a BV-supported antibiotic treatment decision matrix can lead to a significant reduction of antibiotic use without compromising patient safety in an ICU population. If antibiotic exposure is not reduced in the intervention group (non-superior), we would not recommend implementation of the BV test widely. We would evaluate if the finding can be attributed to an unexpectedly lower antibiotic use in the control arm (compared to usual practice in ICU) and would recommend hospitals choose either the BV test or clinical assessment of prescription quality to reduce antibiotic use in ICU. If our findings demonstrate reduction in antibiotic use but evidence of harm in the intervention group, we will not recommend widespread implementation of the BV test but would carefully analyze our adverse outcome results to determine if select events are driving the overall finding. We would further perform subgroup analyses to assess if these outcomes occurred predominantly in specific groups.

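### Section 12.8 states H2 both as no significant difference and as non-inferiority; only the second is the test sized in section 12.4

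*Protocol*

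**What the plan says.** Protocol section 12.4 frames H2 as showing that BV-supported decisions do not worsen clinical outcomes: "We expect a combined adverse outcome rate of 18-20% and will set a non-inferiority margin at 4"%. It continues: "A sample size of 529 patients per group (1060 in total) will therefore provide 80% power to demonstrate H2". Appendix I gives the error rates ("For all calculations below – Type I error = 0.05, Power = 0.8, One-sided test") and shows that 529 comes from an 18% rate with BV against 20% in control.

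Section 12.8 tests H1 (antibiotic exposure) first. If the H1 null is rejected at the first interim, H2 is assessed and the decision to continue depends on it. There H2 is written as "H2: no significant difference in combined endpoint of adverse events between the 2 groups". The closing sentence of 12.8 then expects that H2 may reach non-inferiority only at full enrolment.

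Section 12.9 (Final Analysis) gives no margin, confidence limit or non-inferiority test for H2. It describes a one-sided test of antibiotic duration and a comparison of DOOR distributions, and names chi-square tests for categorical measures in general.

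Section 1.3 (Potential impact) adds: "If our findings demonstrate reduction in antibiotic use but evidence of harm in the intervention group, we will not recommend widespread implementation". It does not say what would be concluded if antibiotic use fell but non-inferiority was simply not shown.

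**The concern.** The two versions of H2 put the burden of proof on opposite sides. Under non-inferiority, H2 is met only when the data exclude an excess of 4 points or more. Under non-significance, H2 is met whenever the data fail to prove harm, and that becomes easier as the sample gets smaller. A paragraph holding both criteria lets the same data be read either way.

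The intervention recommends stopping antibiotics in ICU patients, and safety is half of the primary objective in section 3.2.1. The choice between the two wordings decides whether an excess that the sponsor has set as its limit can be reported as acceptable.

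**Working it through.** **Inputs.** Margin 4 points and expected adverse-outcome rate 18–20% (12.4); one-sided 0.05 and 80% power (Appendix I); 18% v 20% behind the 529 (Appendix I); target 600 per group (4.1), allocated 1:1 (7.1); looks at 1/3 and 2/3 of enrolment (12.7), so about 200 and 400 per group. The two-sided 0.05 case is shown as an alternative, because 12.8 gives no sidedness for its wording.

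**1. The plan's own figure.** With unpooled variance,

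n = (z₀.₉₅ + z₀.₈₀)² × [p_C(1−p_C) + p_B(1−p_B)] / [margin − (p_B − p_C)]²

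= (1.645 + 0.842)² × (0.1600 + 0.1476) / (0.04 + 0.02)² ≈ 6.18 × 0.3076 / 0.0036 ≈ 528.3, rounded up to 529.

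This reproduces the protocol. The other eight H2 rows in Appendix I reproduce within 2 patients by the same formula, so H2 was sized as non-inferiority throughout.

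**2. Harm equal to the margin under the non-significance wording.** Take 20% control and 24% BV at 600 per group.

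- SE under the null (pooled rate 0.22): √(2 × 0.22 × 0.78 / 600) = 0.02392.
- SE under the alternative: √[(0.16 + 0.1824) / 600] = 0.02389.
- One-sided 0.05: Φ[(1.645 × 0.02392 − 0.04) / 0.02389] = Φ(−0.03) = 0.489.
- Two-sided 0.05: Φ[(1.96 × 0.02392 − 0.04) / 0.02389] = Φ(0.29) = 0.613.

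**3. The same harm under the sized test.** The true difference equals the margin, so the chance of passing is Φ[(0.04 − 0.04)/SE − 1.645] = Φ(−1.645) = 0.05 at any n.

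**4. The design case under the sized test (18% v 20%).**

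- 600 per group: SE = √(0.3076/600) = 0.02264; Φ(0.06/0.02264 − 1.645) = Φ(1.005) = 0.843.
- 200 per group: SE = √(0.3076/200) = 0.03922; Φ(0.06/0.03922 − 1.645) = Φ(−0.115) = 0.454.

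**Results, before any interim adjustment:**

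| n per group | Not significant, 24% v 20%, one-sided 0.05 | Same, two-sided 0.05 | Margin test met, 24% v 20% | Margin test met, 18% v 20% |
|---|---|---|---|---|
| 200 | 75% | 84% | 5% | 45% |
| 400 | 61% | 72% | 5% | 70% |
| 529 | 53% | 65% | 5% | 80% |
| 600 | 49% | 61% | 5% | 84% |

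A simulation of 400,000 trials per sample size agreed to within 0.2 percentage points on the non-significance columns and gave about 5% for the margin test at 24% v 20%. With control rates from 15% to 30% at 600 per group, a 4-point harm is non-significant in 42–56% of trials one-sided and 55–68% two-sided.

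**The case against.** The best defence is that the protocol plainly means non-inferiority. Section 12.4, every H2 row of Appendix I and the end of 12.8 say so. The expectation that H2 may be met only at full enrolment makes sense only under that reading, since non-significance is easiest to obtain early. This stands. A reader might infer that the trial's safety conclusion as a whole rests on failing to find a difference; the documents do not support that. What they show is one section contradicting itself and the sizing. The full test specification may sit in an SAP, so the silence of 12.9 is not a fault in itself; it only means that 12.9 does not settle which wording governs.

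Three other strong readings also fail.

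- A reader might say that a margin-sized harm would usually pass. With the protocol's own one-sided 0.05 and 600 per group it is about an even chance (49%).
- A reader might take the 75–84% at the first look as the chance of being declared safe. Section 12.8 ties H2 at the interim only to a decision to continue, without saying which result leads to which action. Nothing says that a non-significant interim difference establishes safety or ends the trial for success, and sections 13.1 and 13.2 provide independent safety monitoring.
- A reader might infer from 1.3 that an inconclusive safety result would still allow a recommendation. That section is a narrative on impact and states no rule for a positive recommendation. The uncovered outcome is also not always likely: in the design case (18% v 20%, 600 per group) it has at most 100% − 84% = 16% probability.

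None of this removes the conflict in 12.8, the section that puts H2 to use.

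**Conclusion.** The point holds as an internal contradiction. Section 12.8 gives H2 two incompatible definitions, and the one attached to the interim decision is not the test that was sized. Following the non-significance wording at full enrolment would pass a harm equal to the margin in about 49% (one-sided) to 61% (two-sided) of trials, against 5% under the sized test, which is roughly a tenfold difference.

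These figures assume a 20% control rate, 600 analysed per group, a normal approximation and no adjustment for the interim looks. The margin, error rate and sample size in 12.4 agree with Appendix I and are not in question here. Section 1.3 is a minor, consequential matter.

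**What to change.** - **12.8 and 12.9:** state that H2 is met only if the upper one-sided 95% confidence limit (or its interim-adjusted counterpart) of the risk difference, BV minus control, is below 4 percentage points. Add that a non-significant difference does not establish H2 at any look.
- **12.8, interim action:** state that missing the bound at an interim means H2 is not yet shown. This is needed because, even in the design case, the unadjusted bound is met only about 45% of the time at 200 per group. Keep any harm criterion for the monitoring committee separate from this success criterion.
- **1.3 (minor):** make a positive recommendation depend on H1 rejected and the bound met, and report non-inferiority not shown as inconclusive on safety.

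The cost is wording only, ideally settled before the first interim look. No new data or patients are needed: power at 18% v 20% is about 84% at 600 per group before interim adjustment. The downside is that more results will be reported as inconclusive. Non-inferiority would not be shown in about 16% of trials in the design case, and in about 46% if both true rates are 20% (the sized test passes 53.5% there at 600 per group).

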11. EVALUATION, RECORDING, AND REPORTING OF ADVERSE EVENTS

In this RCT, the primary safety outcome will encompass all significant potential adverse events related to the cessation or withholding of antibiotics. These adverse outcomes will be integrated into the primary safety outcome measure and will not be reported separately as Adverse Events (AEs) or Serious Adverse Events (SAEs) elsewhere in the study.

Despite our comprehensive approach, unforeseen adverse events may still occur. Therefore, ongoing monitoring of AEs is essential to ensure participant safety and maintain data integrity.

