12.2 Definitions for clinical outcomes and ranking of outcome categories (DOOR)

Points are assigned for overall outcomes, with pre-specified definitions for treatment failure, complications and adverse events related to antibiotic use. All clinical outcomes will be reviewed by a 3-member clinical review panel, and all AE will be reviewed by a different 3-member panel (the Data Safety and Monitoring Committee). The panels will consist of experienced ID, Pharmacy and ICU experts (to be named) blinded to intervention and patient identity.

Clinical outcome	Definition
Treatment failure	Signs and symptoms of initial event (infectious illness) within 72h of end of antibiotic treatment
Infection persistence	Continued presence of signs and symptoms and of original causative pathogen at end of antibiotic treatment
Infection recurrence	New infection due to at least one of the original causative agents found at baseline (initial event)
Infectious complication	Signs and symptoms requiring surgical or other procedure in organ involved in initial event (eg. empyema post pneumonia) occurring >72h after end of antibiotic treatment

We will determine how many DOOR events (AE, infection recurrence etc.) occurred for each participant, then assign a mutually exclusive rank.

RANK	Criteria
1	Survival, clinical benefit of treatment, with NONE of treatment failure, persistence, recurrence, complication AND NONE of Grade IV adverse event (AE)
2	Survival, clinical benefit of treatment, with NONE of treatment failure, persistence, recurrence, complication, AND at least one of AE
3	Survival, at least one of treatment failure, persistence, recurrence, complication, AND NONE of AE
4	Survival, at least one of treatment failure, persistence, recurrence, complication AND at least one AE
5	Death

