13.1 Data Monitoring and Auditing

Data monitoring will be performed by data monitoring study team member based at the central (Glen) site, for completeness and plausibility, logic checks for accuracy, and will send queries to the study nurses in cases of ambiguity or errors. Data documentation will be performed continuously. Data verification for primary outcomes will be a priority.

The study coordinator may perform on-site monitoring of documentation by comparing data entry with source documents (eg. participant records) for completeness and chronology, logic checks for accuracy and trend analysis to identify problem areas. The site PIs will cooperate in resolving any queries or findings made during the monitoring process.

The Data safety and monitoring board (DSMB) will provide independent monitoring of interim results and make recommendations for continuation, modification or termination of the study. The DMSB will meet at two planned interim analyses for safety, at completion, and at any other needed interval.

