13.2 Data Safety and Monitoring Committee (DSMC)

This committee will be composed of at least 3 members, with at least one expert for each of infectious diseases, ICU, and pharmacy. The committee will be independent from the steering committee, and will initially define all the event triggers that would prompt unscheduled review, as well as review of interim and cumulative data for evidence of efficacy and safety. They will review data quality and completeness, factors that might compromise data confidentiality or affect outcomes. They will conclude each review with recommendation to the steering committee whether the study should continue without change, be modified, or terminated.

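### The formal interim comparison of adverse outcomes (H2) is conditional on an antibiotic reduction at the first interim, which conflicts with the unconditional interim safety review in 13.1 and 13.2

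*Protocol*

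**What the plan says.** Protocol 12.7 plans an intent-to-treat primary analysis that "will include 2 interim analyses at 1/3 and 2/3 enrolment", with Lan-DeMets stopping rules. Section 12.8 sets the order of testing. "Should the null H1 be rejected at the first interim, then the second hypothesis" (H2, the combined adverse-outcome endpoint) is assessed, and the decision to continue rests on it. Otherwise: "If H1 is not rejected at the interim, then H2 will not be assessed until the final analysis". The same section adds: "We estimate that H1 testing may cross the pre-specified boundary at one of the interim analyses". It also expects that H2 may reach non-inferiority only at full enrolment.

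The oversight sections read differently. Section 13.1: "The DMSB will meet at two planned interim analyses for safety, at completion, and at any other needed interval". Section 13.2 gives the DSMC the task of defining triggers for unscheduled review, and "review of interim and cumulative data for evidence of efficacy and safety". Neither section mentions H1.

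Two other places bear on the point. Section 11 says that harms from stopping or withholding antibiotics, being part of the primary safety outcome, "will not be reported separately as Adverse Events (AEs) or Serious Adverse Events (SAEs) elsewhere in the study". Section 12.2 names the DSMC as the panel that reviews all AEs and describes the panels as unaware of allocation.

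**The concern.** Testing H1 before H2 is reasonable for claiming non-inferiority, because non-inferior safety is of little interest if antibiotic use has not fallen. It is a poor rule for detecting harm. If antibiotics are stopped in the wrong patients and later restarted for relapse, outcomes can worsen while mean antibiotic days barely change. In that case H1 is not rejected, and 12.8 then puts off the comparison that would show the problem. Section 1.1 notes that critically ill patients were excluded from earlier studies of the test, so its safety in this population is an open question.

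The text is also hard to follow in practice. Under 12.8, an interim report with H1 not rejected contains no H2 comparison. Under 13.1 the same meeting is an interim analysis for safety. The statistician preparing the report cannot tell which section governs. Nor does 12.8 say what to do if H1 first crosses at the second interim: it refers to the first interim, then to the interim without a number, then to either one.

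**Working it through.** **Inputs from the protocol.** 600 per arm (4.1); 1:1 allocation (7.1); interims at 1/3 and 2/3, so 200 and 400 per arm (12.7); one-sided alpha 0.05, 80% power, 1.5-day difference, SD 8 (12.4); SDs of 4 to 10 days (Appendix I).

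**Assumptions.** No spending function is named. That may sit in the SAP and is not counted as a fault, so three common forms are used. Outcomes are taken as complete for the 200 and 400 per arm at each interim.

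**The plan's own figures.**

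H1: n = 2·SD²·(z0.95 + z0.80)²/δ² = 2·64·6.183/2.25 = 351.7, so 352 per group as stated.

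H2 (18% v 20%, margin 4%): n = [0.18·0.82 + 0.20·0.80]·6.183/(0.04 + 0.02)² = 0.3076·6.183/0.0036 = 528.3, so 529 per group as stated.

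**Boundary at the first interim (t = 1/3).**
- O'Brien-Fleming-type: 2 − 2Φ(1.960/√(1/3)) = 0.00069, z = 3.20
- Linear: 0.05/3 = 0.0167, z = 2.13
- Pocock-type: 0.05·ln(1 + (e − 1)/3) = 0.0226, z = 2.00

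**Chance that H1 crosses at the first interim.** The expected z is 1.5/(8·√(2/200)) = 1.875. The crossing probability is 1 − Φ(bound − 1.875):
- O'Brien-Fleming-type: 1 − Φ(1.325) = 9%
- Linear: 1 − Φ(0.253) = 40%
- Pocock-type: 1 − Φ(0.127) = 45%

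**Chance that no interim H2 comparison is made, literal reading** (only a first-interim crossing opens H2):

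| True effect, SD | O'Brien-Fleming-type | Linear | Pocock-type |
|---|---|---|---|
| 1.5 days, SD 10 | 96% | 74% | 69% |
| 1.5 days, SD 8 | 91% | 60% | 55% |
| 1.5 days, SD 6 | 76% | 36% | 31% |
| 1.5 days, SD 4 | 29% | 5% | 4% |
| No reduction | 99.9% | 98.3% | 97.7% |

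**Looser reading** (a crossing at either interim opens H2). Cumulative crossing probabilities by the second interim come from multivariate normal integration. At SD 8 they are 0.696, 0.761 and 0.769 in the same order, which leaves 30%, 24% and 23% with no interim H2 comparison. With no reduction the cumulative alpha spent is 0.016, 0.033 and 0.038, which leaves 98%, 97% and 96%.

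The choice of reading therefore matters a great deal if the planned effect is real. It matters hardly at all if the intervention does not reduce antibiotic use: H2 then almost always waits for the final analysis.

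**The case against.** The strongest reply is that H2 is a formal non-inferiority hypothesis and not the trial's safety monitoring. Monitoring is provided separately: 13.1 has the board meet at both interims and whenever needed, and 13.2 lets the DSMC set triggers, review cumulative safety data and recommend modification or termination. On that view, deferring H2 costs little. Much of this stands. A reader might infer from 12.8 that safety goes unexamined until 1,200 patients are enrolled; 13.1 and 13.2 do not support that. What they do not say is that deaths and the composite are shown by arm when H1 is not rejected, and 12.8 points the other way.

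The second reply is that the probabilities depend on the reading, the SD and the spending function. That stands too. A reader might infer that both interims will most likely pass without an H2 comparison. That holds at SD 8 on the literal reading, only narrowly under Pocock-type spending, and not on the looser reading.

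A reader might also infer from Section 11 that deaths and treatment failures are kept from the DSMC. The text only prevents their being reported twice: outcomes are still collected through Day 28 and adjudicated, and nothing withholds them from the committee.

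Finally, a reader might infer that the DSMC cannot be both a blinded AE panel (12.2) and the interim reviewer (13.2). No section says that it sees unmasked arms, and tables with coded arms would not reveal one patient's allocation. The two roles need reconciling, but a breach of blinding is not shown.

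**Conclusion.** The concern holds as a conflict in the text and a badly placed condition. Section 12.8 ties the formal interim comparison of adverse outcomes to rejection of H1 at the first interim, while 13.1 and 13.2 describe interim safety review that does not depend on H1. The rule for a first crossing at the second interim is unclear.

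At the planning case the literal rule means no interim H2 comparison with probability 55% to 91%, depending on the assumed spending function. The looser reading gives 23% to 30%, and smaller SDs give lower figures under either reading. The least favourable case is one where antibiotic use does not fall: over 97% on the literal reading. That is also a case in which harm could still occur. The relapse and re-treatment mechanism is a plausible argument; the protocol gives no figure for it.

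**What to change.** Before the first interim, amend 12.8 to agree with 13.1 and 13.2, along these lines: *At both interim analyses the DSMC reviews deaths and the H2 composite with its components by arm, whatever the result for H1. This review spends no efficacy alpha. The order H1 before H2 applies only to claiming non-inferiority.* State in the same place whether a first H1 crossing at the second interim opens the formal H2 test.

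As a secondary change, reconcile 12.2 with 13.2. Either have the existing blinded clinical review panel adjudicate AEs as well, or state that the DSMC sees coded arms.

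The cost is amendment wording, one extra table per interim report and, if AE adjudication moves, some added work for the clinical panel. The sample size and the alpha for H1 are unchanged.
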